### SUMMARY

# **Official Title**

The Effectiveness and Safety of Triple 2ml Hyaluronic Acid Intra-articular Injection (Suplasyn®) in Managing Symptomatic Primary Osteoarthritis of the Knee in Real-life Practice: ESTIK Survey.

# **Study Officials/Investigators**

Orthopeadists/Traumatologists

### **Review Board**

All study materials have been approved by the Ethical Committee for Clinical Investigation of the Krnov Hospital (The Czech Republic).

### **Primary Outcome**

To assess changes in clinical outcome of patients with OA recommended with a triple Suplasyn® 2ml injection for viscosupplementation.

### **Intended Intervention:**

Suplasyn® 2ml during 3 weeks for the viscosupplementation of the knee.

### **Study Type:**

Observational, non-interventional, international and multicenter study.

### **Study Design**

Observational Model: Case-Only; Time Perspective: Prospective study

# **Condition for Study**

Osteoarthritis of the Knee.

# Study sample

Patients over 18 years old with Primary Knee Osteoarthritis (Kellgren's grades I to III) without effusion.

# **Data Monitoring**

Clever Instruments S.L. will be in charge of logistic and clinical trial monitoring.

# Calendar

Study Start Date: June, 2014 - September, 2014

Study Completion Date: December, 2014 - March, 2015

Overall study period will be of 6 months, approximately.

### 1 GENERAL INFORMATION

# **Official Title**

The Effectiveness and Safety of Triple 2ml Hyaluronic Acid Intra-articular Injection (Suplasyn®) in Managing Symptomatic Primary Osteoarthritis of the Knee in Real-life Practice: **ESTIK Survey**.

# **Study Officials/Investigators**

Orthopeadists/Traumatologists

### **Duration of the Study**

Intended duration: 6-9 months

Data will be provided by investigators from retrospectively results observed in patients who were previously recommended with viscosupplementation with Suplasyn® between June-September 2014 and December 2014-March 2015.

The assignment of the patient to a particular therapeutic strategy should not be decided in advance by this protocol but falls within current practice and the use Suplasyn® was clearly separated from the decision to include the patient's data in this study.

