# 5.2 Study Design

Observational Model: Case-Only; Time Perspective: Prospective study

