**CONFIDENCIAL** 

injection of Hyaluronic Acid (Suplasyn®) once per week during a 3 three weeks period. All patients who received the specific recommendation are includable for study.

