# **Eligible patients:**

Ages: 18 years to 85 years

Genders: Both

- Accepts Healthy Volunteers: No

- Study Population: Patients with symptomatic primary knee OA, with radiological grades I to III (according Kellgren-Lawrence Score) and without clinical effusion at time of inclusion.

All patients whose data will be recorded should have been informed by the researcher of the nature of the study and that his/her participation is voluntary. Registration of their data has to be started as long as he/she has signed the consent form and has clearly understood all the study procedures. Consent form could be obtained orally as long as the researcher asks for a witness to sign (i.e. nurse or patients' relative).

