# **Exclusion Criteria:**

- Allergic reactivity to hyaluronic acid
- Current knee infection, infection around injection site or any skin disease
- Pregnancy or lactation
- Participating in other clinical trial
- Any reason that may jeopardize the collection of data (patient likely to be lost-to-follow up)

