# 9 PRACTICAL CONSIDERATIONS

# 9.1 Work plan

All researches will have to register to be assigned with a personal id and password for access to study online surveys. Once the researcher has signed the *researcher commitment form* and have received a confirmation of his/her registration can proceed to the inclusion of data.

Patients will be selected from those who accomplish inclusion criteria, based on the consecutive sampling technique. Researcher will proceed to explain patient about the study and ask for a signature on the *consent form* prior to the inclusion.

It is important to keep in mind that the recommendation with Suplasyn® for the viscosupplementation of the affected knee is not conditioned to the development of the study or the inclusion of a specific patient in this study.

Data will be recorded by the researcher in an online electronic Case Report Form (eCRF) to which will access with their id and password. The online platform will assign to each patient an automatic and unique code which will allow registering his/her clinical information throughout all study visits for the later generation of a database and an analysis of the final results. The eCRF does not contain any patients' personal information and the researcher is committed to keep the access information and the content of the eCRFs in complete anonymity, besides the obligation to accomplish with the principles and laws applicable in his/her local context, being fully responsible for the truthful of the provided data.

- On visit 1 (baseline) patient will receive the first intraarticular injection of 2ml of Hyaluronic
  Acid Suplasyn® in the affected knee following the product instructions leaflet and according to
  standard measures for these types of procedures. In this visit, patient will also have to complete
  the Patient eCRF which includes the OKS.
- On visit 2 (administration of the second HA injection, one week after first injection) and Visit 3 (administration of the third HA injection, one week after second injection) adverse events should be investigated. In case the researcher obtains as a response to the question

"How did you feel since your last visit" any adverse event since prior visit, the *Adverse Event* Form should be completed and sent to the study coordinator.

- Visit 4 (1 month after injection): Researcher will complete the eCRF corresponding to that
  visit by recording data on patient's consumption of any pharmacological treatment for pain

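### Section 1 describes data collected retrospectively from patients already recommended the product, which contradicts the prospective, consent-first, consecutive design in the rest of the protocol

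*Protocol*

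**What the plan says.** Section 1, under Duration of the Study, describes the source of the data: "Data will be provided by investigators from retrospectively results observed in patients who were previously recommended with viscosupplementation". It dates those recommendations by two windows, June to September 2014 and December 2014 to March 2015. The next paragraph, partly in the past tense, says that "the use Suplasyn® was clearly separated from the decision to include the patient's data in this study".

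The rest of the protocol reads differently:

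- Summary (Study Design) and Section 5.2: "Observational Model: Case-Only; Time Perspective: Prospective study".
- Section 5.3, Eligible patients: "Registration of their data has to be started as long as he/she has signed the consent form".
- Section 9.1: the researcher must explain the study and "ask for a signature on the *consent form* prior to the inclusion". On sampling: "Patients will be selected from those who accomplish inclusion criteria, based on the consecutive sampling technique".
- Section 9.1, visit 1: the first injection and the patient's own electronic form, including the OKS, belong to the same visit.
- Section 6.2: patients complete the OKS and the VAS at baseline, 1 month and 6 months.
- Section 5.4: follow-up runs 26 weeks from the first injection.
- Section 7.2: the primary endpoints are changes from baseline in OKS and VAS pain at 4 and 26 weeks.
- Summary, Calendar: the same two windows appear as the study start and study completion dates.

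**The concern.** The protocol gives two incompatible answers to one question: is the outcome already known when a patient's data enter the study?

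Read plainly, Section 1 puts the results first and the decision to include the data afterwards. Sections 5.2, 5.3 and 9.1 put consent, registration and baseline first and the results afterwards.

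Two things are at stake. First, both primary endpoints need a baseline that the patient filled in before treatment. A self-completed OKS and a mark on a 100 mm line cannot be created once the result has been observed. Second, the study has one arm. If patients who did well were more likely to be entered, no comparator would absorb the difference, and it would appear as treatment effect.

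**Working it through.** **1. The texts side by side**

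| Question | Section 1 | Rest of the protocol |
|---|---|---|
| Direction of data | Retrospective, results already observed | Prospective (Summary, 5.2) |
| Consent and registration | Not mentioned; inclusion of data follows use of the product | Consent before registration (5.3) and before inclusion (9.1) |
| Sampling | Patients previously recommended the product | Consecutive among eligible patients (9.1) |
| Baseline OKS and VAS | Could not be self-completed at the right time | Completed by the patient at baseline (6.2); OKS named at visit 1 (9.1) |
| Meaning of the two windows | Period of past recommendations | Study start and study completion (Summary, Calendar) |

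Section 8.4 does not bridge the gap. It places the inclusion decision after the recommendation, which fits prospective entry. It does not place it after observed results.

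**2. The dates.** Follow-up is 26 weeks, or 26 × 7 = 182 days (Section 5.4).

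- Start window plus 182 days: 1 June 2014 gives 30 November 2014, and 30 September 2014 gives 31 March 2015. This is the completion window almost to the day.
- If patients were recommended and first injected in the second window, 1 December 2014 gives 1 June 2015 and 31 March 2015 gives 29 September 2015. Both fall after the stated completion.

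The windows therefore work as an enrolment and completion calendar. They do not work as a period of recommendation.

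**3. What selection could do (illustration only).** The protocol gives no expected change and no SD. Section 5.6 gives only an estimated 300 patients, so there is no planned figure to reproduce.

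Assume the VAS improvement is normal with mean μ and SD σ. All patients above the mean are entered, and a fraction a of those below it. The two halves have means μ ± σ√(2/π), with weights 1 and a, so

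observed mean = μ + σ × 0.798 × (1 − a)/(1 + a).

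With μ = 15 mm and σ = 25 mm (assumed):

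- a = 0.8: 0.798 × 25 × 0.2/1.8 = 2.2, observed 17.2 mm.
- a = 0.6: 0.798 × 25 × 0.4/1.6 = 5.0, observed 20.0 mm, which is 5.0/15 = one third too high.

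The added amount does not depend on μ and scales with σ. At σ = 20 mm it is 1.8 and 4.0 mm; at σ = 30 mm it is 2.7 and 6.0 mm. With n = 300 and σ = 25, the standard error is 25/√300 = 1.44 mm, so the shifts are 2.2/1.44 = 1.5 and 5.0/1.44 = 3.5 standard errors.

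A second model leaves out the worst fraction p entirely. The bias in SD units is φ(z_p)/(1 − p): 0.11, 0.20 and 0.35 for p = 5%, 10% and 20%. Against 1/√300 = 0.058 SD, that is 1.9, 3.4 and 6.1 standard errors. In neither model does a larger sample reduce the bias.

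**The case against.** The strongest reply is that this is one badly worded sentence under a heading about duration, set against every operative section. The dates support that. The windows are those of the Summary calendar, and they fit 26 weeks of forward follow-up. The paragraph after the sentence makes the usual non-interventional point, which Sections 8.4 and 8.7 also make. A site working from Section 9.1 would obtain consent, enter patients consecutively and collect the questionnaires as visits occur. All of this stands as an account of what was probably meant. It does not remove the contradiction, because nothing in the protocol says which text governs and a site could cite Section 1 for entering completed cases.

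A reader might go further in three ways that the documents do not support.

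- **That the protocol allows investigators to choose patients by outcome.** It nowhere says so. Section 1 speaks of patients recommended, not explicitly treated, although observed results imply treatment. Outcome-informed entry is an inference from following Section 1, and consent before registration, consecutive sampling and a visit-1 questionnaire all work against it.
- **That the exclusion criterion is a second contradiction.** Section 5.3 says "All patients who received the specific recommendation are includable for study" and later excludes for "Any reason that may jeopardize the collection of data (patient likely to be lost-to-follow up". The first is a general statement that the inclusion and exclusion lists then narrow. The exclusion is a judgement made at entry, before any outcome exists. It may limit generalisability, but it is not selection on response.
- **That the millimetre figures estimate a bias in this study.** They presuppose the selective entry they illustrate, and every input is assumed.

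**Conclusion.** The sentence in Section 1 is wrong as written and must be reconciled with Sections 5.2, 5.3, 6.2 and 9.1. The contradiction is textual and needs no assumption. The risk to the primary result is conditional: if a site followed Section 1, inclusion could be decided with results known and the baseline would not be valid, which could bias the change in both OKS and VAS. The size of that bias cannot be derived from the documents. The 17.2 and 20.0 mm show only that moderate selection could exceed the sampling error at n = 300. They rest on an assumed mean of 15 mm, an SD of 25 mm, normality and the stated entry rates, and they cover VAS only.

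**What to change.** - In Section 1, delete the retrospective sentence and restate the two windows as the enrolment and completion calendar given in the Summary.
- In Section 9.1, state that each patient is registered in the electronic case report form, with a system date stamp, after the recommendation and consent and before the first injection, and that the baseline OKS and VAS are completed then.
- State that patients registered after the first injection are left out of the primary analysis.
- Optionally, have sites keep a short anonymous count of recommended patients not entered, with the reason, so that consecutive sampling can be checked.

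The exclusion for likely loss to follow-up can stay. The cost is a few lines of rewording, a date check in the electronic form and, if adopted, a brief count at each site. Some late-registered patients may be lost from the primary analysis. Treatment and visit schedule do not change.

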# 2 BACKGROUND

Osteoarthritis (OA) of the knee is a painful and disabling condition that is becoming more prevalent in patients over 50 years of age that results in symptoms in 10% of people older than 55 years which severely impair up to a quarter overall these patients. (1)

OA is generally treated using conservative measures at initial phases of the disease (2), more frequently with analysics, topical and oral non-steroidal anti-inflammatory drugs (NSAIDs). However, their long-term use of these agents might different organic risks such as complications in hepatic, cardiovascular, gastrointestinal or renal systems.

In recent years, viscosupplementation has been more often used as a therapeutic modality for the management of knee OA (3,4). Intra-articular injections of Hyaluronic Acid (HA) have shown good safety profiles and efficacy for treating knee OA pain. Recent clinical data have demonstrated that anti-inflammatory and chondroprotective effects of HA viscosupplementation are associated with a significant and maintained reduction on pain up to 14-26 weeks after injection while improving patients' function (5-7), results which show a clear difference compared to the short-term effect of other interventions such as pharmacological treatment with NSAIDs and/or corticosteroid injections.

### Viscosupplementation

Viscosupplementation is intended as an alternative of HA's degradation in the synovial fluid of patients affected with knee osteoarthritis by the administration of exogenous HA through intra-articular injection. Viscosupplementation is recommended (6) for the treatment of knee OA by the current Osteoarthritis Research Society International (OARSI) Guidelines and previous practice guidelines (4,8-11) and despite that in other reference documents such as current Clinical Practice Guidelines (CPG) of the American Academy of Orthopaedic Surgeons (AAOS) is not included as a main recommendation(12), this makes reference to published evidence reporting significant improvements on OA symptoms after viscosupplementation. Because of the lack of evidence and the possible discrepancies across studies, conclusion should be as that viscosupplementation may be of significant benefit for *some* patients (13).

Administration of an exogenous HA cannot explain long-term reduction of symptoms, considering that HA has short half-life. HA has biological effects on the inflammatory cells and

stimulates HA production by synovial cells. Its key molecular role in joints' biomechanics explains how a reduction in its concentration and molecular weight greatly alters the properties of synovial fluid, causing cartilage damage and worsening osteoarthritis symptoms (14). Treatment with exogenous HA attempts to restore the elasticity and viscosity of synovial fluid to normal levels, resulting in pain reduction and functional improvement. Different studies have also confirmed that HA interacts with mediators of inflammation and matrix turnover in joint cells. HA has also a biosynthetic chondroprotective effect (15-20).

Identification of CD44, a glycoprotein expressed on the cell surface of chondrocytes, may explain HA interaction with chondrocytes since CD44 is considered a HA's receptor at the chondrocyte cell surface so the provision of exogenous HA into articular cartilage is facilitated through this receptors (21,22).

### **Triple versus Single Injection**

Study assessing five different dosing regimens of viscosupplementation suggests that  $3 \times 2ml$  injections one week apart are efficacious and well tolerated (25). Multidosage viscosupplementation (3-6 injections) still remains a golden standard if choosing the viscosupplementation as a treatment for knee OA.

The single injection represents a new alternative to the three injections treatment regimen with documented statistically and clinically significant improvements (30) both in pain and physical function in patients with knee OA (23), however its efficacy, safety and long-term effect should be studied in order to establish if this newly introduced approach is comparable with the proven triple injections regimen (26).

#### Suplasyn® 2ml and 1-shot (6ml)

Suplasyn® is a low-intermediate molecular weight HA (500-1000 kDa) product which is safe and well tolerated (24). Suplasyn® is a CE marked Medical Device (CE0473) and is approved by in several countries for the treatment of pain associated with knee osteoarthritis. The recommended treatment regimen for the treatment of knee osteoarthritis pain is one 2 ml intra-articular injection per week for three consecutive weeks (28) or a single injection of 6ml (33,34).

Both presentations are supplied as pre-filled syringes containing 20mg/2ml of sodium hyaluronate which is administered according to a dosing regimen of one injection per week for three to six consecutive weeks.

Suplasyn® has shown to be more effective than placebo on pain and function in knee osteoarthritis (24) with similar efficacy when compared to NSAIDs (27) and with maintained effects over the long term (28). These studies also demonstrated its excellent safety profile.

Suplasyn® has also demonstrated useful health economic benefits with a reduction in the costs of management of knee OA during the 26-weeks following the course of viscosupplementation (29).

### **Study Rationale**

The current study is designed to assess the effectiveness and safety of Suplasyn® 2ml injections in a 26-week, international, multicenter, non-interventional observational study of patients recommended with one 2 ml intra-articular injection of Suplasyn® per week for three consecutive weeks with for the treatment of knee osteoarthritis. The intention is to assess the efficacy and safety of the treatment in real-life practice. Our primary target is to obtain and verify long-term outcomes from a naturalistic primary care experience.

Rationale for using viscosupplementation is to restore the protective viscoelasticity of synovial hyaluronic acid, decrease pain and improve mobility. Immediate benefit of viscosupplementation is the relief of pain while long-term benefits results are believed to include the return of joint mobility by the restoration of trans-synovial flow and the metabolic and rheological homeostasis of the joint (31). Short duration of HA within the joint does not fully explain the indisputable long-term clinical efficacy seen in practice (32).

In this case, it is appropriate to evaluate, under real-life conditions, the short-term and long-term effectiveness of triple Suplasyn® 2ml intra-articular injections and to how the extended treatment regime may impact patient satisfaction or treatment safety.

### 3 OBJECTIVES

# 3.1 Main Objective

To assess changes in clinical outcome of patients with OA recommended with a triple Suplasyn® 2ml injection for viscosupplementation.

# 3.2 Secondary Objectives

- To evaluate the safety profile and adverse events (AEs) of Suplasyn® 2ml injections.
- To evaluate the concomitant consumption of permitted rescue medications (analgesics, NSAIDS) throughout the study.
- To evaluate characteristics of the beneficiary population (Intended to treat).

# 4 SOURCE OF INFORMATION

All data will be provided by the researcher and by the patients who assist to the orthopedist/traumatologist with a symptomatic knee OA and according to physician criteria could be recommended with viscosupplementation with Suplasyn®.

# 5 STUDY DESIGN

### 5.1 Study Type:

Observational, non-interventional, international and multicenter study.

# 5.2 Study Design

Observational Model: Case-Only; Time Perspective: Prospective study

# 5.3 Study population

#### Main Selection Criteria:

Patients consulting to the orthopedist/traumatologist to primary care centers and according to specialist evaluation are susceptible of been recommended with viscosupplementation through a intraarticular

**CONFIDENCIAL** 

injection of Hyaluronic Acid (Suplasyn®) once per week during a 3 three weeks period. All patients who received the specific recommendation are includable for study.

# **Eligible patients:**

Ages: 18 years to 85 years

Genders: Both

- Accepts Healthy Volunteers: No

- Study Population: Patients with symptomatic primary knee OA, with radiological grades I to III (according Kellgren-Lawrence Score) and without clinical effusion at time of inclusion.

All patients whose data will be recorded should have been informed by the researcher of the nature of the study and that his/her participation is voluntary. Registration of their data has to be started as long as he/she has signed the consent form and has clearly understood all the study procedures. Consent form could be obtained orally as long as the researcher asks for a witness to sign (i.e. nurse or patients' relative).

#### **Inclusion Criteria:**

- Age between 18 and 85 years old
- Primary osteoarthritic degeneration of the knee (patients with documented knee osteoarthritis)
- Patients fulfilling criteria for primary knee osteoarthritis, radiological grades I–III (Kellgren– Lawrence) (35) and joint space width ≥2 mm
- Patients without clinical effusion at baseline
- Fully aware of study procedures
- Willing to participate in all study processes and assessments

